### ***5.3 Interim Monitoring Plan***

The DSMB for the Consortium will have overall responsibility for monitoring the emerging results. For this and other trials conducted by the Consortium members, the focus of the DSMB will be on safety issues, recruitment, retention, protocol adherence and data quality and timeliness. The DSMB will meet at least twice each year and more frequently if needed.

Since the enrollment period is relatively short and planned analyses will be conducted by the Consortium, using outcome data from all of the centers, no interim monitoring for efficacy will be undertaken. Thus no group sequential stopping rules are specified. Any explicit stopping rules for harm will be determined by the DSMB. In addition, futility as defined by low conditional power to show a benefit given the outcome data to date will not be assessed. However, recruitment will be monitored by the DSMB and the recommendations of the group will be sought if accrual is falling below the goal needed to complete the project by the conclusion of funding.

For each meeting, a formal detailed statistical report will address all aspects of the trial, including baseline variables, outcome variables, compliance with the protocol, data quality, loss to follow-up (primary outcome missing), and protocol violations (such as randomization of ineligible patients). Outcomes will be reported in a cohort of patients randomized before a given date. All adverse events reported to date will be included, with an indicator showing new events since the previous meeting. Adverse events may be reported to some or all of the DSMB members on a more frequent basis if applicable, as requested by the DSMB.

Only outcome variables primarily assessed for safety reasons will be reported by treatment group, including inadequate weight gain for mother and infant. The DSMB will not be masked to group, unless specifically requested.

The DSMB will also consider new information from external sources such as the results of other randomized trials and results of meta-analyses of similar interventions. If this new information is judged relevant to all patients, the DSMB may recommend changes to the protocol or to the consent form.

### ***5.4 Analysis Plan***

All statistical analyses will be based upon the total cohort of patients randomized into the trial. Although data on some patients may be missing, all relevant data available from each patient will be employed in the analyses. Patients will be included in the treatment group to which they were randomly assigned regardless of the adherence to the intervention.

The primary analysis will consist of a simple comparison of GWG using an independent t-test. While this is a longitudinal study, and taking advantage of second trimester weights would be a more powerful analysis, there is currently no indication that the pattern of weight gain (whether excess weight gain occurs in the second trimester or third) is associated with worse outcomes. As the intent of this trial is to limit GWG, the analysis is designed to specifically address the comparison of mean weight gain in the two groups. Mean and standard deviation of weight gain will be reported. If the groups are found to differ on a pre-treatment factor known to be a factor related to weight gain, the statistical analysis will adjust for these differences using a multiple linear regression model. Additionally, adjusted means and confidence intervals will be presented after adjusting for factors such as age, pre-pregnancy BMI, and race.

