### 2.2 Potential for Prevention

**Studies on Prevention of Excessive GWG: Results and Limitations.** Behavioral interventions on diet and increased physical activity in nonpregnant obese adults have successfully achieved weight loss and improved clinical outcomes, such as reduced incidence of type 2 diabetes (T2D); but far less is known about behavioral interventions in pregnant women. Trials conducted to date have yielded mixed results; some but not all intervention trials have succeeded in reducing GWG in OW/OB women [24-27]. Pre-pregnancy BMI, smoking habits, race, income and number of prior pregnancies were all associated with GWG, but not all studies controlled for these factors [22, 24-27]. One randomized controlled trial (RCT) among low income women, intervened with biweekly newsletters, personalized weight gain charts and individualized nutrition counseling and reported decreases in GWG among normal weight but not overweight women [22]. More recent results using a similar intervention also reported improved postpartum weight loss maintenance in both normal weight and OW/OB women [28]. Conversely, intervention with educational radio broadcasts, pamphlets, supermarket tours, cooking demonstrations, exercise groups and individual counseling geared toward healthy diet and exercise during pregnancy was

not associated with significantly reduced GWG compared to the control group [24]. Reduction of GWG in a low income subgroup of normal and OW women was achieved by charting weight gain and providing five 1-page mailings about healthy eating and exercise during pregnancy [25]. A Finnish study that individualized counseling on diet and physical activity following five routine OB clinical visits along with group exercise sessions did not affect excessive GWG but intake of vegetables, fruit and dietary fiber increased [27]. Still another study reported reduced GWG in OB women through weekly 30-minute individual motivational sessions and aqua aerobic classes designed for OB women conducted by nurse midwives [29]. While these studies offer potential promise, well-designed studies with adequate power and standardized methods are needed to enhance adherence to lifestyle interventions and document reductions in excessive GWG in large, ethnically diverse populations and also sustain these behavioral changes postpartum.

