### 5.2 Sample Size and Power

The proposed total sample size for MOMFIT is 300 women, with 150 randomized to Active Intervention and 150 to the Control Group. Because this study compares two randomized groups, power is based on an independent 2-sample t-test using a two-sided type I error rate ( $\alpha$ ) of 0.05. Assuming a SD of 15lbs (6.8kg) of GWG, a sample size of 143 women per group is sufficient to attrition to provide 80% power to detect a difference of 5 lbs (2.4 kg) between groups. A difference of 5 lbs was chosen to be clinically significant. It is expected that there will be no more than 5% attrition from randomization through 36 weeks and delivery; thus a total sample size of three hundred patients was chosen.

The anticipation is for no more than 10% attrition for secondary outcomes measured at delivery, and no more than a 20% attrition rate from randomization to 12 month postpartum. **Table 5** shows the specific aims, attrition, and effect sizes detectable for secondary outcomes with 80% power for a sample size of 300 women based on two-sided t-tests and Chi-square tests of association ( $\alpha=0.05$ ).

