#### ***5.4.1 Methodology***

In general, analyses of data will be conducted to address the primary and secondary research questions of the trial, and other interrelationships among elements of study data of interest to the investigators and of relevance to the objectives of the study. Specifically when comparing groups multiple linear or logistic models will be fit. A further exploration of weight gain and retention will be examined using mixed models to determine if the patterns of weight gain and loss are similar across the two groups.

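### The primary t-test is followed by a balance-triggered adjustment rule with no threshold, closed factor list or stated status, so the plan does not say which result decides if the two disagree

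*Combined protocol and SAP*

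**What the plan says.** Section 5.4 is direct about the main test: "The primary analysis will consist of a simple comparison of GWG using an independent t-test". Its brief reason is that "the analysis is designed to specifically address the comparison of mean weight gain in the two groups". Section 5.2 sizes the trial on the same basis: "power is based on an independent 2-sample t-test using a two-sided type I error rate", with the result that "a sample size of 143 women per group is sufficient to attrition to provide 80% power to detect a difference of 5 lbs".

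Section 5.4 then adds the conditional rule: "If the groups are found to differ on a pre-treatment factor known to be a factor related to weight gain, the statistical analysis will adjust", by multiple linear regression. The next sentence adds an unconditional analysis: "Additionally, adjusted means and confidence intervals will be presented after adjusting for factors such as age, pre-pregnancy BMI, and race".

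Five other places touch on covariates:
- Section 5.4.1: "Specifically when comparing groups multiple linear or logistic models will be fit". It names no covariates and gives the models no status.
- Section 5.4.2 says the design controls for race/ethnicity. However, section 3.6 has no stratification, and a t-test has no race term.
- Section 5.5 keeps gestational age at delivery out of the primary analysis. It is the only covariate that the plan rules out.
- Section 2.2, as background: "Pre-pregnancy BMI, smoking habits, race, income and number of prior pregnancies were all associated with GWG, but not all studies controlled for these factors". Section 3.4.4 excludes current smokers, and this list omits age, which section 5.4 names.
- Sections 3.4.2 and 4.3 show that BMI, date of birth, race/ethnicity, income and parity are collected before randomization.

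**The concern.** The conditional sentence says that the analysis will adjust, so it is an instruction and not an option. Three things are needed to carry it out, and the plan does not supply them: what counts as a difference (a p-value, a standardized difference or a judgement), which factors are checked, and whether the regression then takes the place of the t-test.

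In a randomized trial any imbalance at baseline is due to chance, so the undefined threshold and list decide how often the rule fires. When it fires, the trial has two estimates and two p-values for its single primary hypothesis. If they fall on opposite sides of 0.05, the plan does not say which one stands, and the choice would be made with both in view. A balance-triggered rule also captures little of the precision that adjustment for a fixed list can give.

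**Working it through.** **1. Reproduce the plan's figure.** Inputs from section 5.2: difference 5 lb, SD 15 lb, two-sided alpha 0.05, 143 per group.
- Standard error = 15 × √(2/143) = 1.774 lb. Noncentrality = 5/1.774 = 2.819, with 2 × 143 − 2 = 284 df.
- Noncentral-t power is 80.2% (79.9% at 142 per group), so 143 reproduces.
- 95% CI half-width = 1.968 × 1.774 = 3.49 lb.

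**2. How often the rule fires.** For k independent factors and trigger level a, the chance is 1 − (1 − a)^k. The plan gives neither k nor a, so both are assumed.

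| Factors checked | p<0.05 | p<0.20 |
|---|---|---|
| 3 | 14% | 49% |
| 5 | 23% | 67% |
| 10 | 40% | 89% |

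**3. How often the two results disagree.** Simulation with 20,000 trials per setting, 143 per arm, true difference 5 lb, and five independent normal covariates sharing R² equally. The regression adjusts for each covariate whose baseline p-value is below the trigger. The documents give no R², so a range is shown. The entries are the percentage of all trials in which the t-test and the triggered regression fall on opposite sides of p = 0.05.

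| Assumed R² | 0.02 | 0.05 | 0.10 | 0.20 |
|---|---|---|---|---|
| Trigger p<0.05 | 1.0 | 1.8 | 2.1 | 2.9 |
| Trigger p<0.20 | 2.6 | 4.3 | 5.1 | 7.3 |

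Among the trials in which the p<0.05 rule fires, disagreement is 4.5%, 7.9%, 9.6% and 13.1%.

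**4. Type I error with no true difference.**
- Rule followed mechanically, same R² values: 5.0%, 4.7%, 4.7%, 4.6% (trigger p<0.05) and 5.0%, 4.6%, 4.4%, 4.1% (trigger p<0.20). There is no inflation.
- Freedom to report either the t-test or the triggered regression: 5.3% to 6.0% (R² 0.1 and 0.3, both triggers).

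**5. Power if a fixed list is always used.** The error variance is 225 × (1 − R²), with 284 − p df for p covariate degrees of freedom. Power is averaged over chance correlation between arm and covariates. The t-test comparison is 80.2%.

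| Assumed R² | 0 | 0.02 | 0.05 | 0.10 | 0.20 |
|---|---|---|---|---|---|
| 5 df | 79.5% | 80.3% | 81.5% | 83.5% | 87.5% |
| 7 df | 79.2% | 80.0% | 81.2% | 83.2% | 87.3% |

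Break-even R² is 1.8% with 5 df and 2.5% with 7 df. In step 3, at R² 0.20 and the p<0.05 trigger, simulated power was 80.0% for the t-test, 80.6% for the triggered rule and 87.1% for adjustment for all five covariates. The trigger therefore recovers little of the available gain.

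**The case against.** The best defence is that the status is largely settled. Section 5.4 labels the t-test primary, section 5.2 powers on it, and the further adjusted means are introduced as an addition. The factors are also not wholly open: the rule is limited to known correlates of weight gain, section 5.4 names three examples, and section 2.2 gives background candidates. With three factors and a p<0.05 trigger the rule fires in only about 14% of trials, and the larger disagreement rates need an assumed p<0.20 trigger. Much of this stands, and it limits the point to an ambiguity. It does not remove it, because the conditional sentence is mandatory, has no status of its own, and no other section gives it one.

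A second objection is that replacing a valid, adequately powered test is a matter of preference, and that this version is late. It is dated May 28, 2016. Section 8.1.2 targeted the last randomization for September 2014, and section 8.1.3 expected primary-aim data by May 2015. A new primary analysis at that stage could look data-driven. This also stands, and it shapes the fix.

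A reader might infer that the rule biases the trial, inflates type I error or leaves it underpowered. The documents do not support this: the planned power reproduces, and the rule applied as written is level or slightly conservative. Nor do they show that anyone has seen outcome data by arm. The dates only make it possible.

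**Conclusion.** The concern holds as an avoidable ambiguity over which result decides, with some precision left unused. It should be corrected, but it does not threaten the validity of the named t-test. Its size is disagreement in about 1% to 3% of trials (p<0.05 trigger) or up to about 7% (p<0.20 trigger), and a false positive rate of about 5% to 6% if either result may be reported. These figures rest on five independent normal covariates, assumed triggers and an assumed R². Correlated or categorical covariates would change them somewhat. Larger inflation, 6.5% to 7.8%, appears in the same simulations only with a free choice among the t-test, the triggered model and a fully adjusted model. That is a stronger reading than the text supports, since one of the three is named primary.

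**What to change.** 1. Delete the conditional sentence in section 5.4.
2. State that one named analysis alone decides the primary hypothesis, whatever the observed baseline balance.
3. Replace the open list of adjustment factors with a closed list of covariates collected before randomization, for example age, BMI (saying which measure), race/ethnicity and parity. Gestational age at delivery stays out, as section 5.5 requires.
4. If no outcome data by arm have been seen, the fixed-list regression can be the deciding analysis, with the t-test as support. If such data may have been seen, keep the t-test as the sole deciding analysis and present the fixed-list regression as supporting.

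No new data are needed. Keeping the t-test leaves power at 80.2%. Making the regression decisive costs a few degrees of freedom. The example list uses 1 + 1 + 3 + 1 = 6 if race/ethnicity has four groups (an assumption), so the 7 df figures slightly overstate the cost. With 7 df it gains power if the covariates explain more than about 2.5% of the variance, and otherwise loses at most about 1 point (79.2% against 80.2%). The change is one paragraph of wording, but section 7.2.4 requires DSMB approval of major protocol changes, and a new primary analysis may count as one.

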#### ***5.4.1 Methodology***

In general, analyses of data will be conducted to address the primary and secondary research questions of the trial, and other interrelationships among elements of study data of interest to the investigators and of relevance to the objectives of the study. Specifically when comparing groups multiple linear or logistic models will be fit. A further exploration of weight gain and retention will be examined using mixed models to determine if the patterns of weight gain and loss are similar across the two groups.

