### 3.2 Secondary Research Questions

- Will adherence to the DASH diet and lifestyle intervention, in addition to reduced GWG, also produce postpartum weight control and other beneficial outcomes related to the following parameters?
- Will metabolic profiles (blood pressure, anthropometry, fasting glucose, insulin or C-peptide, HbA1c, blood lipids and CRP) of mothers and babies be different between the Intervention and Usual Care groups?
- Will prenatal diet and lifestyle intervention in overweight/obese mothers result in fewer complications of pregnancy (preeclampsia, gestational diabetes mellitus (GDM), cesarean birth)?
- Will infants in the Intervention group breastfeed longer, begin solid foods later and have higher quality diets (more fruits, vegetables, dairy, less sugary beverages) than Usual Care group infants at 12 months?
- Is adiposity (percent body fat) and body weight reduced postpartum in mothers and babies in the intervention group compared to Usual Care?
- Do mothers in the Intervention group have higher quality diet (more fruits, vegetables, grams of fiber and nonfat dairy; less saturated fat/trans fat, sugar sweetened beverages) and more minutes of physical activity than mothers in the Usual Care group throughout the study?
- Will diet quality differences be evident as measured by metabolomics assays specifically related to fruit/vegetable and dietary fiber intake as alkylresorcinols (fiber), prolinebetaine (citrus fruit) and S-methyl-L-cysteine sulphoxide (cruciferous vegetables) in maternal urine and cord blood.
- Are measures of sleep quality and duration, depression and stress, self-efficacy and mindfulness in diet, breastfeeding and physical activity more favorable in the intervention group compared with the Usual Care group?

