**Waist and Hip Circumference** will be measured using standardized methods at the 6 week and 12 month postpartum visits for the mothers.

**Height** will be measured with a stadiometer at the Baseline visit only, according to the CARDIA standardized protocol.

**Blood Pressure.** (BP) will be measured at each clinic visit (Table 3), baseline, 24-28 weeks, 35-37 weeks, 6 weeks and 12 months postpartum. Seated BP will be measured after a 5 minute rest according to a standardized protocol. Systolic and diastolic (5th phase) BP will be measured three times, one minute apart, using an Omron® automated BP device. Participants with DBP  $\geq$  100 mmHg or SBP  $\geq$  180 will be referred for medical attention immediately.

**Phlebotomy.** Fasting (8hr) samples of serum and plasma will be collected for storage at baseline, 35-37 weeks, 6 weeks and 12 months postpartum. If needed a 2hr OGTT will be done on participants with a fasting, 1hour and 2 hour blood draw. This would be in lieu of the 1 hour at their OB/GYN.

At the Baseline visit, HbA1c will be analyzed for eligibility. All other blood will be stored for future analysis of glucose, insulin, HbA1c, CRP, lipid panel (total cholesterol, triglycerides, HDL-C, calculated LDL-C), vitamin D and other potential biomarkers. Some of these markers (lipids) are altered by pregnancy but these will be used to compare groups. All samples will be promptly placed in melting ice and centrifuged (2500 for 20/min) within 2 hours of collection. This volume of blood drawn is safe in pregnancy. The changes in glucose from baseline to 24-28 and 36 weeks and the frequency of GDM in the two groups provide secondary endpoints/outcomes.

**Spot urine for mothers** will be collected at all data collection visits and stored for purposes of metabolomic measures to be assessed as exploratory aims and provide possible preliminary data regarding possible diet-influenced changes observed between groups.

**Breastmilk** will be collected among participants who choose to breastfeed at the 6 week and 12 months postpartum visits for purposes of comparing in both groups, the nutrient quality of the mothers' diet with the nutrients measured in breast milk, and also the nutrients measured in the cordblood and infant's blood. Samples of 50-150 mL (approximately 1.5-4.5 fl oz) of early (6week ) and mature (12 month) breastmild will be collected and stored in the Northwestern repository.

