**Mindful Eating Questionnaire (MEQ).** The construct of mindfulness refers to a nonjudgmental awareness of physical and emotional sensations associated with eating that, if recognized may help a person identify and respond appropriately to satiety [59-62]. A 28 item scale was developed and validated by Framson, et al [63] as an initial step towards characterizing and measuring mindful eating. It addresses disinhibition, awareness, external cues, emotional responses and distraction but is distinct from cognitive restraint. LIFE Moms can assess and differentiate over time whether the role of mindful eating plays a role in facilitating adherence to an energy balanced diet.

**SF-12 Health Survey (SF-12) [64].** The SF-12 is a 12-item self-report measure of quality of life. It was derived from the original 36-item measure, and taps a variety of domains including physical functioning, bodily pain, general health, vitality, social functioning, physical and emotional functioning, and mental health functioning. The SF-12 also provides two composite indices of physical health and mental health. *Estimated completion time: 5 minutes*

**Breastfeeding** will be measured using three questions adapted from the Southampton Women's Survey [65] and CDC Infant Feeding Practices study [66]. The questions assess initiation and duration of breastfeeding [66], duration of exclusive breastfeeding [65], and timing of introduction of water and complementary fluids [65]. The questions will be administered between postpartum weeks 48 and 56. Breastfeeding status will be confirmed at the 6 week post-partum visit.

**Infant Food Intake The infant Food Frequency Questionnaire by LIFE-MOMS (FFQ).** Long-form is a dietary assessment instrument to characterize infants' food intake during the first year of life. The long FFQ was assembled by Life-Moms based on a published shorter version, expanding the 19 categories to include 54 food items with a brief description on how these were prepared and/or their source (e.g., raw, canned, etc.). Previous infant studies were used to identify these food items, with particular emphasis to include typical Hispanic foods. It also includes information on supplements use. A food database will be

created to calculate nutrient intake for the long FFQ. The long FFQ is interviewer or self-administered and is a pen-and-paper or a web-based instrument.

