#### ***4.7.4 Infant Secondary Outcomes***

- a) weight
- b) length
- c) sum of skinfolds
- d) duration of breastfeeding
- e) infant age at which solid foods were introduced
- f) diet quality
- g) physical activity

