Under intention-to-treat principles, all participants will be included in the analysis. Missing data related to the primary outcome will be evaluated to assess whether the missing mechanism may be ignorable or non-ignorable [74-76]. If the missing data mechanism is judged to be ignorable, where appropriate, analyses involving mixed models may be used such that all existing values are analyzed, and no observations are deleted due to missing values. Alternatively multiple imputation may be carried out to create several complete data sets. For each complete data set, overall tests of interest for the outcome will be conducted and the results of each combined to create a single test result. For completeness, a pattern-missing analysis should be conducted to investigate non-ignorable missingness. If the missing data mechanism is likely to be non-ignorable, multiple imputations can be conducted using a version of the approximate Bayesian bootstrap based on distance-based selection criteria [77]. Sensitivity analyses under various assumptions regarding the missing data will be conducted to confirm the robustness of the results.

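### Breastfeeding duration is right-censored at the 12-month visit, but the plan names only linear or logistic models, which cost some power and leave the target quantity undefined

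*Combined protocol and SAP*

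**What the plan says.** - **Outcome.** Section 4.7.4 lists "duration of breastfeeding" among the infant secondary outcomes. Section 3.2 asks: "Will infants in the Intervention group breastfeed longer, begin solid foods later and have higher quality diets".
- **Measurement.** On the breastfeeding questions, section 4.4.3 says: "The questions will be administered between postpartum weeks 48 and 56". Table 4 places the breastfeeding questionnaire at 12 months only. The one earlier item is a status check: "Breastfeeding status will be confirmed at the 6 week post-partum visit".
- **Ongoing breastfeeding.** Section 4.4.3 says breast milk "will be collected among participants who choose to breastfeed at the 6 week and 12 months postpartum visits". Table 3 repeats the 12-month collection, and Table 2 has breast-milk rows for the second six months.
- **Method.** Section 5.4.1: "Specifically when comparing groups multiple linear or logistic models will be fit". Mixed models are added there for weight gain and retention only.
- **Incomplete data.** Section 5.4 promises that "all relevant data available from each patient will be employed in the analyses". The imputation and mixed-model text in section 5.4.3 starts from the primary outcome: "Missing data related to the primary outcome will be evaluated to assess whether the missing mechanism may be ignorable or non-ignorable". Section 5.4.4 has censoring in its title, but its analysis rules deal only with the last weight and with who stays in the intention-to-treat analysis.

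Nowhere do the documents name a time-to-event method. They do not say what duration is entered for a mother still breastfeeding at the interview, or for one seen at 6 weeks and then lost.

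**The concern.** A mother who is still breastfeeding at the interview has no duration yet, only a lower bound that depends on where in the 48-to-56-week window she was seen. A linear model has to treat that bound as a stopping time or leave the mother out. It also has no place for a mother known only to have been breastfeeding at 6 weeks. A logistic model avoids the cut-off by fixing a time point, but then does not compare durations.

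At stake are the power of one secondary comparison that the intervention targets directly, and clarity about what is estimated. Without a stated rule, the analyst decides after the data are in whether ongoing durations are capped, dropped or censored, and these choices give different answers.

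**Working it through.** **Inputs from the documents.** 150 women per arm; two-sided alpha 0.05; attrition to 12 months of at most 20%, and at most 10% for outcomes at delivery (section 5.2); interview at weeks 48 to 56 and status at 6 weeks (section 4.4.3).

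**Assumptions, because the documents give no breastfeeding rates.** Exponential durations; hazard ratio of stopping 0.70; control mean 20, 30 or 40 weeks; interview uniform over weeks 48 to 56; 20% lost at random after the 6-week visit.

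**Step 1: the plan's own figures.** There is none for breastfeeding, so only the general settings can be checked.
- Primary outcome: n per group = 2 × (1.960 + 0.842)² × 15² / 5² = 141.3, so 142. The exact t-test gives 142.2, rounded up to the stated 143.
- Table 5 at 12 months: 300 × 0.80 = 240, or 120 per arm. The detectable effect is 2.802 × √(2/120) = 0.362 (0.363 with the t-test), against the stated 0.37.

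**Step 2: what the linear model estimates.** For an exponential duration with mean m, the mean up to week τ is m × (1 − exp(−τ/m)), and the share still breastfeeding at τ is exp(−τ/m). The intervention mean is m/0.70. Example with m = 30 (intervention 42.86):
- τ = 52: 30.12 − 24.70 = 5.42 weeks.
- τ = 48: 28.87 − 23.94 = 4.93 weeks.

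| Control mean (weeks) | Still breastfeeding at week 52, control / intervention | Full difference | Restricted to 52 weeks | Linear estimate, simulated | Restricted to 48 weeks |
|---|---|---|---|---|---|
| 20 | 7% / 16% | 8.6 | 5.4 | 5.5 | 5.1 |
| 30 | 18% / 30% | 12.9 | 5.4 | 5.4 | 4.9 |
| 40 | 27% / 40% | 17.1 | 5.0 | 5.1 | 4.5 |

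The linear estimate matches the 52-week restricted mean difference. It is far from the full difference, but that column extends the exponential curve beyond the last interview, where the trial has no data.

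**Step 3: power.** Two separate simulations gave the ranges below. The log-rank test uses all women and censors the lost ones at 6 weeks if they were still breastfeeding.

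| Control mean (weeks) | Linear, completers | Log-rank, all women | Gain (points) |
|---|---|---|---|
| 20 | 71–72% | 75–77% | 4–5 |
| 30 | 63% | 70–71% | 7–8 |
| 40 | 54–57% | 62–66% | 8–9 |

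Placing half of the 20% loss before the 6-week visit keeps the gain within 4 to 9 points. A wider set, with control medians of 3, 6, 9 and 12 months, gave:
- linear: 72%, 57%, 48%, 38%;
- log-rank in completers: 74%, 63%, 55%, 44%;
- log-rank in all women: 77%, 66%, 56%, 45%;
- comparison of proportions breastfeeding at 6 months: 58%, 44%, 35%, 28%.

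The total gain is again 5 to 9 points, of which keeping the lost women supplies about 1 to 3. With no true effect, every method rejected in 4.6% to 5.2% of trials.

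**Step 4: why a rule is needed.** For the same four medians, with complete follow-up and a fixed 12-month cut-off, capping gives differences of 1.24, 1.19, 1.00 and 0.85 months. Treating ongoing durations as missing gives 0.64, 0.39, 0.27 and 0.20. The plan does not say it would do the latter, but nothing excludes it.

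**Step 5: loss related to early stopping.** If mothers who stop before 3 months are lost more often (assumed 35% against 12%), completer means rise by about 0.3 to 0.4 months in each arm. The capped difference changes little: 1.26, 1.13, 0.95 and 0.78 months.

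**The case against.** Three stronger readings are tempting, and the documents support none of them.

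- **The plan's estimate is biased towards no effect.** That holds only if the target is full duration and a linear model is used. The plan states no such target, and the research question closes with a reference to 12 months, although that phrase may belong only to diet quality. Against a 12-month restricted mean the capped difference is unbiased under complete follow-up or random loss. It even slightly exceeds the 48-week restricted mean recommended below. The method sentence in section 5.4.1 is also generic, and a logistic comparison at a fixed time is untouched by the cut-off, at lower power.
- **Mothers lost after 6 weeks are discarded.** No passage says so, and section 5.4 promises the opposite. What stands is that the named models give no means of keeping that promise for a bare 6-week status.
- **The loss is large.** The 20% runs from randomization, which is 60 of 300 women. At the planned ceilings 10%, or 30 women, are already allowed for by delivery, so only about half of the loss falls later and could leave a 6-week status.

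It is also fair to say that exponential durations with proportional hazards favour the log-rank test, that the milk collection is conditional on mothers choosing to breastfeed, and that this is one of many secondary outcomes without a power claim in Table 5. These points limit the size. They do not supply the missing censoring rule.

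**Conclusion.** The point holds as a modest one about a secondary outcome. Durations still running at the 48-to-56-week interview are right-censored, and the only comparison methods named cannot represent that. A linear analysis of capped durations would be a valid test of a 12-month restricted mean difference, but with about 4 to 9 points less power than a censoring-aware test, and for a quantity the plan never defines. The range rests on the assumed exponential durations, control means of 20 to 40 weeks, hazard ratio of 0.70 and 10% to 20% loss after the 6-week visit. The actual share still breastfeeding at the interview is not in the documents. Neither the primary analysis nor the 143 per group is affected.

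**What to change.** Add to section 5.4.1:

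- Analyse duration of any breastfeeding, counted from birth, as time to stopping. Show Kaplan-Meier curves, compare groups by log-rank test or Cox model, and report the restricted mean difference to 48 weeks, the earliest interview date.
- Censor mothers still breastfeeding at the interview on the interview date.
- Censor mothers lost after the 6-week visit at that visit only if they were still breastfeeding then. Treat a mother who had already stopped, with no recorded stop date, as an event interval-censored between birth and 6 weeks.
- Add a sensitivity analysis for loss related to early stopping.
- Use the same approach for exclusive breastfeeding and age at first solids, for consistency. The plan's feeding advice places both transitions at around 4 to 6 months, so no 12-month censoring bias is claimed for them.

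The cost is a short paragraph of text. No new visits or data are needed.
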